9.3 Sample size

We have estimated that 20% of fistulas fail early and that early ultrasound has a positive predictive value (number of true positives/number of predicted positives, PPV) of 72% for predicting non-maturation. To estimate this with $\pm 10\%$ precision (i.e. the 95% confidence interval is from 62% to 82%), 78 predicted failures are required. We estimate that US predicts failure in 25% of fistulas, therefore, 312 fistulas overall are required. Allowing for 10% dropout, 347 fistulas are required. We anticipate that two models to predict primary fistula patency will be required and therefore we will have two PPVs- one for wrist fistulas and one for elbow fistulas. Assuming a ratio of 50:50 for wrist to elbow fistulas, the precision confidence interval will be from 55.3% to 85.2%.

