9.5.1 Analysis of primary and secondary outcomes

The primary fistula patency rate by week 10 will be calculated alongside an exact 95% confidence interval based on all participants enrolled. It will also be calculated based on participants whose fistulas did not fail early.

The secondary outcomes will be presented using descriptive summary statistics.

Mixed multivariable logistic regression will be used to model primary fistula patency by 10 weeks to develop a model, which can be used as a risk-score calculator in the phase 2 trial (not part of this protocol). Two models will be built, one for wrist fistulas and one for elbow fistulas. Measurements taken from the first scan performed at week 2 will be considered as parameters in the model initially and further parameters from either the second scan or the third scan will then be considered. The choice of second or third scan will be based on the best fitting parameters, as assessed by significance level. A random effect for patient will be included in the models to account for multiple scan data per participant. The aim will be to build parsimonious models, which contain the minimum number of measurements, required to effectively predict primary fistula patency. A receiver operating characteristic

(ROC) curve analysis of the developed risk scores will be used to assist decisions regarding an appropriate cut-off for an indicator for when intervention is required for both wrist and elbow fistulas. The PPV will be calculated alongside an exact 95% confidence interval for the chosen risk-score cut-off.

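### The PPV and its exact 95% CI are calculated on the same fistulas that choose the predictors, the scan and the cut-off, so the PPV is biased upward and the interval usually under-covers

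*Protocol*

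**What the plan says.** Section 9.3 sizes the study on the precision of a PPV. It assumes that "early ultrasound has a positive predictive value (number of true positives/number of predicted positives, PPV) of 72% for predicting non-maturation", concludes that "78 predicted failures are required", and continues: "We estimate that US predicts failure in 25% of fistulas, therefore, 312 fistulas overall are required". It then expects a separate score for each site: "We anticipate that two models to predict primary fistula patency will be required". With a 50:50 split it gives a per-model interval of 55.3% to 85.2%.

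Section 9.5.1 describes how each score is made. Week-2 measurements are considered first, then measurements from one later scan: "The choice of second or third scan will be based on the best fitting parameters, as assessed by significance level". The models are to be parsimonious, and a ROC analysis of the resulting scores helps to set the cut-off. The last step is: "The PPV will be calculated alongside an exact 95% confidence interval for the chosen risk-score cut-off".

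Section 9.5.2 includes all recruited participants where possible. It also says that levels of missing data will be considered when the scan is chosen. Section 1.4 makes phase 2 conditional on ultrasound being found effective at identifying at-risk fistulas.

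**The concern.** The exact (Clopper-Pearson) interval treats the number of true failures among flagged fistulas as binomial under a rule that was settled before these fistulas were seen. Here three features of the rule are tuned to the same fistulas on which the PPV is then counted: which measurements enter, which later scan is used, and where the cut-off lies. Each choice favours chance patterns that make the flagged group look richer in failures. The apparent PPV is therefore optimistic, and the interval is centred too high and ignores the variation due to selection.

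The PPV is the quantity the study is sized to estimate, it informs the move to phase 2, and the score itself is meant to serve as the phase 2 risk calculator. Optimism would carry into both.

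Significance level is also a weak basis for choosing between scans. It depends on the number of fistulas as well as on discrimination. Thrombosed fistulas get no further study scans (sections 1.4, 6.1 and 6.3), so the week-4 and week-6 data need not come from the same fistulas.

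**Working it through.** **1. The plan's own figures (section 9.3).** Inputs: PPV 72%, half-width 10 points, 25% flagged, 10% dropout, 50:50 split.
- Flagged fistulas: 1.96² × 0.72 × 0.28 / 0.10² = 77.4, rounded up to 78.
- Fistulas: 78 / 0.25 = 312; 312 / 0.90 = 346.7, rounded up to 347.
- Per model: 312 / 2 = 156 fistulas, of which 156 × 0.25 = 39 flagged. The exact interval for 0.72 × 39 = 28.08 of 39 is 55.3% to 85.2%.

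All figures reproduce. The arithmetic is right, but it is the arithmetic of a rule fixed in advance.

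**2. Failures available per model.** The protocol supports a range:
- 20% failing early (section 9.3): 156 × 0.20 = about 31.
- Section 1.4: one-year patency of about 55%, with about 60% of failures in the first three months. This gives 0.45 × 0.60 = 27%, or 156 × 0.27 = about 42.
- As many as 50% failing to mature (section 1.2): 156 × 0.50 = 78.

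**3. Predictor strength implied by the plan.** Flagging 25% with a PPV of 72% gives 0.25 × 0.72 = 18% true positives. Against 20% failures, that is a sensitivity of 0.18 / 0.20 = 90%. The plan thus assumes strong predictors, so the strong-predictor rows below are closest to it.

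**4. Simulation.** Each run had 156 fistulas, backward selection at p < 0.05 on scan 1, then the better of scan 2 or 3 (by AIC), then a cut-off. The PPV with its Clopper-Pearson interval was taken in the same data and compared with the PPV of that rule in 100,000 new fistulas (400 runs per setting). The number of markers, signal strength, selection method and cut-off rule are assumptions, because the protocol does not give them.

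| Failures; signal | Markers per scan | Cut-off | Apparent PPV | True PPV | Optimism (points) | Coverage |
|---|---|---|---|---|---|---|
| 20%; very strong | 2 | 25% flagged | 74.2% | 71.7% | 2.5 | 94.8% |
| 20%; very strong | 4 | 25% flagged | 74.4% | 71.7% | 2.8 | 93.5% |
| 20%; very strong | 8 | 25% flagged | 74.2% | 71.2% | 3.0 | 91.7% |
| 20%; very strong | 4 | Youden | 78.3% | 72.5% | 5.7 | 91.2% |
| 20%; very strong | 8 | Youden | 78.4% | 72.9% | 5.4 | 89.2% |
| 20%; strong | 4 | 25% flagged | 67.4% | 63.4% | 4.0 | 92.7% |
| 20%; strong | 4 | Youden | 67.6% | 62.0% | 5.6 | 91.2% |
| 35%; weaker | 4 | Youden | 66.4% | 58.6% | 7.8 | 79.7% |

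(Differences are from unrounded values.) Over all 36 settings, which also included a cut-off chosen for the highest PPV, the apparent PPV exceeded the true one every time, by 2.5 to 13.0 points. Coverage was below 95% in 33; the other three gave 96.0%, 96.8% and 98.0%.

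Two further sets of runs agree:
- With 3 or 5 markers and 20% or 35% failures (24 settings), optimism was 1.6 to 7.4 points with a fixed flagged share (coverage 90% to 98%) and 4.3 to 9.1 points with a Youden cut-off (coverage 80% to 90%).
- With 4 markers, the scan chosen by smallest p-value and failures varied from 20% to 50%, optimism was 2.7 to 6.5 points (coverage 90% to 93%) and 5.4 to 8.1 points (coverage 79% to 87%) respectively. More failures do not remove the bias.

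**5. Control.** With model and cut-off fixed in advance, bias was -0.8 points and coverage 96.0%. The problem comes from the selection, not from the exact interval as such.

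**6. Does correction work?** A bootstrap that repeated all the selection steps (strong signal, 4 markers) moved the mean PPV from 68.0% to 65.6% (true 64.7%) with 25% flagged, and from 69.7% to 64.7% (true 63.8%) with Youden. Remaining optimism was 0.9 points in both. Splitting the sample instead would leave 39 / 2 = 19.5 flagged fistulas per model, with an exact interval of about 47% to 90% at a PPV of 72%.

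**The case against.** Section 9.5 calls itself brief and defers detail to a statistical analysis plan, which may well add internal validation. That stands: the absence of a validation method from the protocol is not the finding. But section 9.5.1 does state the estimator and the interval, and section 9.3 sizes the study on that interval, so a later plan that put this right would have to replace the protocol's sentence.

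Under the assumptions closest to the plan, the bias is about 2.5 to 5.7 points, against a declared per-model half-width of about 15 points. This also stands, and it limits the size. It does not excuse a bias that runs in a known direction and can be corrected cheaply.

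Several stronger readings are tempting and should be resisted:
- **That the PPV decides whether phase 2 starts.** Section 1.4 states no PPV threshold and requires a separate protocol and application. Section 14.1 foresees a meeting to consider progression. The PPV informs the decision.
- **That the simulations reproduce the stated procedure.** The protocol names neither backward selection at 5% nor a ROC-optimal cut-off; ROC analysis only assists a judgement. The simulations used ordinary logistic regression, without the planned random effect or imputation.
- **That optimism of 8 points or more is to be expected.** A moderate-signal setting gave an apparent PPV of 48% against 39% to 40% in new patients (coverage 81% to 84%), but those PPVs are far from the planned 72%.
- **That significance is the only basis for the scan choice.** Section 9.5.2 also takes missing data into account. It does not deal with the different sets of non-thrombosed fistulas.

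**Conclusion.** The concern holds for two sentences of section 9.5.1: the PPV with an exact interval at a cut-off derived from the cohort, and the scan choice by significance level. Followed as written, they give an upward-biased PPV and an interval that usually covers less than its nominal 95%.

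Assuming about 3 to 6 measurements per scan and selection at 5%, the optimism is about 2 to 7 points with coverage of about 89% to 98% when a fixed share is flagged (25% in the plan). With a Youden-type cut-off it is about 4 to 9 points with coverage of about 79% to 90%, reaching 91% to 92% in some strong-predictor settings. These sizes depend on the number and strength of the markers, the failure rate and the cut-off rule. The direction was the same in every setting examined. Under-coverage is mild when predictors are few and very strong. The sample-size arithmetic is not in question.

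**What to change.** In section 9.5.1, replace the sentence on the PPV and exact interval. For each model, report an optimism-corrected PPV with a bootstrap interval, from internal validation that repeats predictor selection, scan choice and a pre-specified cut-off rule in every resample. The apparent PPV with its exact interval may be shown beside it, labelled as apparent.

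Choose between the second and third scan by optimism-corrected predictive performance on the same set of fistulas, not by significance level, together with the review of missing data already stated in section 9.5.2. Shrinkage is optional and not part of this fix; ridge in particular keeps every measurement, against the stated aim of using as few as possible.

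Cost: the cut-off rule must be fixed before the data are seen, because an assisted judgement cannot be repeated in resamples. Some computing time is needed. The reported PPV will be a few points lower and its interval wider. No extra patients are needed.

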9.5.2 Analysis Population and Missing Data

All recruited participants will be included in the analyses, where possible.

Data management will regularly review the data and missing/anomalous data will be queried with the sites.

It is anticipated that some participants will not attend all scans and therefore some scan data will be missing. Levels of missing data will be summarised for each of the scan time points and will be considered when choosing which scan results to use in the final model. Any missing primary and secondary outcome data will not be imputed. Missing data for parameters in the modelling of primary fistula patency will be imputed using multiple imputation if the level of missing data is greater than 10%.

10. Ethical and Regulatory Issues

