During a trial scan, the AVF is seen to be thrombosed, in which case this information would be shared with the clinical care team to enable appropriate care to continue. In such cases, no further study scans would be required. Clinical outcome data will still be collected at week 10.

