6.1 Study Assessment Schedule

TIMEPOINT*	Screening	Enrolment	AVF Surgery Study Day 0	Week 2 Study Day 14 (+/- 6 days)	Week 4 Study Day 28 (+/- 6 days)	Week 6 Study Day 42 (+/- 6 days)	Week 10 Study Day 70 (+/- 6 days)
Eligibility Screen	X						
Informed Consent		X					
Collect demographics and medical history		X					
Collect operative data			X				
ASSESSMENTS							
Doppler Ultrasound Scan of AVF [^]				X	X	X	X
Clinical Assessment of suitability of AVF for dialysis							X
Routine Assessment of AVF	(as per participating centre standard of care)						

*All timepoints are measured from the date of AVF creation.

^D Informed consent should be obtained prior to any trial procedures (see protocol section 4 for full details on consent procedure).

^Participants found to have a thrombosed AVF will require no further study scans.

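### The imputation rule does not except scans that are absent because the fistula has thrombosed, and the later-scan model and its PPV are not limited to fistulas still open

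*Protocol*

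**What the plan says.** **Scans after thrombosis.** The schedule in Protocol section 6.1 notes: "Participants found to have a thrombosed AVF will require no further study scans". Section 1.4 says of a thrombosis seen at a study scan: "In such cases, no further study scans would be required. Clinical outcome data will still be collected at week 10". Section 6.3 repeats this.

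**Missing data.** Section 9.5.2 gives one reason for missing scans: "It is anticipated that some participants will not attend all scans and therefore some scan data will be missing". Missing model parameters "will be imputed using multiple imputation if the level of missing data is greater than 10" per cent. No rule is given at or below that level. For outcomes: "Any missing primary and secondary outcome data will not be imputed". On the population: "All recruited participants will be included in the analyses, where possible". Levels of missing data at each scan "will be considered when choosing which scan results to use in the final model".

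**Model and PPV.** Section 9.5.1 starts from the week-2 scan, after which "further parameters from either the second scan or the third scan will then be considered". It then chooses a risk-score cut-off and reports the PPV with an exact interval. Leaving out early failures is mentioned only for the patency rate, not for the model or the PPV.

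**Outcome.** The Definitions section ends primary patency at thrombosis. Section 5.1 defines the primary outcome by week-10 diameter and flow thresholds.

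**The concern.** Multiple imputation estimates a value that exists but was not observed. An occluded fistula has no patent-vessel diameter or flow at a later date, and the event to be predicted has already happened. Followed as written, the rule would create such values.

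There is a second route. The scan that detects the thrombosis is observed. If that is the scan chosen for the extended model, the fistula enters with a recorded absence of flow, which predicts its own failure trivially.

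By either route, a lost fistula can be counted as a correctly predicted failure. Section 9.5.1 intends the model as the phase 2 risk calculator, with a cut-off for when to intervene, and section 1.4 makes phase 2 conditional on ultrasound identifying fistulas at risk. The PPV that matters is the one among fistulas still open at the scan.

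Scan choice is also touched. Absences by design accumulate, so week 6 has at least as many as week 4. Part of the missing-data level considered in choosing a scan is therefore a count of failures.

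**Working it through.** **1. The plan's own figures (section 9.3).** Inputs: PPV 72%, precision ±10 points, 25% flagged, 20% failing early, 10% dropout.
- Flagged fistulas: 1.96² × 0.72 × 0.28 / 0.10² = 77.4, so 78.
- Fistulas: 78 / 0.25 = 312. With dropout: 312 / 0.90 = 346.7, so 347.
- Per model: 39 flagged. The exact interval with 0.72 × 39 = 28.08 true positives is 55.3% to 85.2%.

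All of these reproduce.

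**2. Accuracy implied by those figures.**
- True positives: 0.72 × 78 = 56.16. False positives: 78 − 56.16 = 21.84.
- Failures: 0.20 × 312 = 62.4. Non-failures: 249.6.
- Sensitivity: 56.16 / 62.4 = 0.90. False-positive rate: 21.84 / 249.6 = 0.0875.

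**3. Restriction to open fistulas.** Let f be the share of failures already thrombosed before the later scan. The protocol does not give f, so 10%, 25% and 50% are assumptions. Suppose the 72% includes these fistulas.
- Failure prevalence among open fistulas: 0.20(1 − f) / (1 − 0.20f).
- Method A keeps the cut-off, sensitivity and false-positive rate: PPV = 56.16(1 − f) / [56.16(1 − f) + 21.84].
- Method B assumes that every thrombosed fistula was flagged. With T = 62.4f, PPV = (56.16 − T) / (78 − T).

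| f | Share of all fistulas | Prevalence, open | PPV, method A | PPV, method B (exact 95% CI) |
|---|---|---|---|---|
| 10% | 2% | 18.4% | 50.54 / 72.38 = 69.8% | 49.92 / 71.76 = 69.6% (57.6 to 79.9) |
| 25% | 5% | 15.8% | 42.12 / 63.96 = 65.9% | 40.56 / 62.40 = 65.0% (51.9 to 76.6) |
| 50% | 10% | 11.1% | 28.08 / 49.92 = 56.3% | 24.96 / 46.80 = 53.3% (38.2 to 68.0) |

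**4. The reverse case.** Suppose 72% is the true PPV among open fistulas, with 78 flagged. Adding T known failures, all flagged, gives (56.16 + T) / (78 + T):
- T = 6.24: 74.1%
- T = 15.6: 76.7%
- T = 31.2: 80.0%

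**5. The imputation trigger.** Ten per cent is 31.2 of 312 fistulas, or 15.6 of 156 per model. Thromboses at 2%, 5% or 10% of all fistulas do not exceed it alone, and the detecting scans are observed, so fewer values are absent than fistulas are thrombosed. In these scenarios, missed visits would have to add to the total before imputation starts. The observed no-flow route needs no trigger.

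**The case against.** Section 9.5 calls itself a summary, with detail left to a full SAP. How an occlusion is coded is ordinary SAP detail. Since section 9.5.2 speaks of missed visits, its imputation rule may have been meant only for those. Section 6.2 records when a fistula is no longer patent, so the cases can be identified from data already collected. The share thrombosed early has no support in the document, and open but immature fistulas also count as failures. If the share is small, the PPV moves by only about 2 points.

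Much of this stands, and it limits the size. It does not remove the point: section 9.5.2 states a rule that covers these values and keeps all recruited participants where possible, and section 9.5.1 sets no restriction to open fistulas.

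A reader might infer more than the document supports:
- **That thrombosed fistulas are dropped at or below 10% missing.** No rule is stated there. Dropping would also take them out of the later-scan model and PPV; its harm would be lost failures and precision, not an inflated PPV.
- **That thrombosis alone triggers imputation, or that a particular number of failures will carry imputed values.** Step 5 shows otherwise for the first, and the second cannot be derived.
- **That missing data decides the scan.** Section 9.5.1 bases the choice on best fit by significance; missing data is an additional consideration.
- **That the 10% rule implies large complete-case losses across independently missing parameters.** Section 9.5.2 ties missing data to whole unattended scans.

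**Conclusion.** The concern holds in limited form. Scans after thrombosis are absent by design, the imputation rule does not except them, and the later-scan model and PPV are not restricted to fistulas still patent. Fistulas already lost can enter by imputation or through the observed detecting scan, and either way inflate the PPV for the fistulas phase 2 could treat.

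The direction is clear under one condition: thrombosis counts as primary-outcome failure. The Definitions section implies this, but section 5.1 does not say it. A thrombosed fistula needs no week-10 scan, and missing outcomes are not imputed. If its outcome were treated as missing, it would leave the model.

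The size is an illustration only. Over the assumed range of f, the overstatement runs from about 2 points to 16 (method A) or 19 (method B). Only the 50% scenario exceeds the planned ±10 points. The document does not establish that the PPV among open fistulas will be 56%, or any other single value, nor whether the planned 72% includes thrombosed fistulas.

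**What to change.** In Protocol sections 9.5.1 and 9.5.2, and in the SAP, state that:
- thrombosis is a known failure of the primary outcome and is not missing data;
- scans after thrombosis are excluded from imputation and from the missing-data level considered when choosing the scan;
- the later-scan model and its PPV include only fistulas patent at that scan;
- week 4 and week 6 are compared on the same open fistulas;
- earlier thromboses are reported separately and counted as failures in the overall patency rate.

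This is wording only. Recruitment, the scan schedule and data collection do not change, since the time at which patency is lost is already recorded. The cost is fewer failures in the later-scan model, a wider interval and a less favourable PPV. Under method B, flagged fistulas fall from 78 to about 72, 62 or 47 over the assumed range, across both models.

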10.1 Compliance

This study complies with the Declaration of Helsinki (2013). It will also be conducted in compliance with the approved protocol, the principles of Good Clinical Practice (GCP), the UK Data Protection Act, the General Data Protection Regulation and the UK Policy Framework for Health and Social Care Research.

10.1.1 Site Compliance

The site will comply with the above regulations and guidelines. An agreement will be in place between the site and NHSBT, setting out respective roles and responsibilities.

The site will inform the CTU as soon as they are aware of a possible serious breach of compliance, so the CTU can report the breach if necessary, within 7 days as per the UK regulatory requirements. For the purposes of this regulation, a serious breach is one that is likely to affect to a significant degree:

- The safety or physical or mental integrity of the subjects in the trial, or
- The scientific value of the trial.

10.1.2 Data Collection and retention

CRFs, clinical notes and administrative documentation should be kept in a secure location (for example, locked filing cabinets in a room with restricted access) and held for 10 years after the end of the study. During this period, all data should be accessible to the competent authorities and the Sponsor with suitable notice.

10.1.3 Access to Data

Custody of the final data set will reside with the Chief Investigator and NHSBT CTU (for audit purposes). Access to the final data set for additional analyses will be permitted under the agreement of the Trial Steering Committee, according to the publication policy in

